3. STUDY DESIGN

3.1.1

Participants

99 stroke patients with dysphagia after an acute/subacute unilateral hemispheric infarction, presenting at Beth Israel Deaconess Medical Center (BIDMC) will be prospectively enrolled, if eligible, into the study. All stroke patients admitted to our hospital receive a standardized dysphagia screening using a bedside water swallow test and are referred for a swallow evaluation to a speech and language pathologist (SLP) if suspected of having dysphagia. Those with moderate to severe dysphagia (PAS ≥ 4) on a standardized videofluoroscopic swallowing (VFSS) evaluation will be invited for participation if they fulfill all study criteria. The patient as well as the SLP will be blinded to the stimulation allocation. Subjects will be randomly assigned to the two intervention or sham groups using PROC PLAN in SAS using a blocking scheme with block size of 6. Subjects will be stratified based on their baseline PAS score (4-6 vs. 7-8) before randomization to the three treatment groups.

3.1.2

Outcomes

Primary Efficacy Outcome: Penetration-Aspiration Score [PAS]: This is a validated 8 point ordinal scale that quantifies penetration and aspiration events observed during VFSS. Since aspiration after stroke is a major predictor of prolonged dysphagia and leads to dietary restrictions, increases the risk of pneumonia and need for tube feeding, this scale will be a relevant measure of swallow status. We have adopted a cut off PAS score ≥ 4 for study enrolment, as minor degrees of penetration can be seen in normal individuals. An average PAS score will be computed based on 5 swallows but if a specific bolus presentation is withheld due to safety concerns, the missing value will be replaced with the worst score (8) for that item.

Primary Safety Outcome: The major safety outcome measures will be **seizures, neurological and motor deterioration or stroke specific mortality** during the period of active stimulation. In light of our small sample size and low expected number of adverse events, we will rely on data from historical cohorts to derive our cut-off numbers for study suspension.

a. Seizures: We expect that a seizure provoked by tDCS would occur during the stimulation session and not thereafter. However, we will analyze the incidence of seizures during the 5 days of active stimulation since excitability changes from tDCS can be prolonged.

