Baseline Comparability: While no substantial differences between treatment groups are anticipated given randomization, we will use summary statistics, graphical techniques such as boxplots, and univariate analyses to compare the baseline characteristics of treatment groups. Pre-treatment values will be compared between the placebo- and tDCS-groups using Analysis of CoVariance (ANCOVA) or the Mantel-Haenszel chi-squared test, as appropriate, to determine if the groups are balanced with respect to baseline characteristics while accounting for stratification by dysphagia severity. This comparison will allow us to identify potential confounders to be included in multivariate analyses.

Analytic plan Primary Aim. Primary analysis will use an intent-to-treat approach; thus all randomized subjects will be used in the primary analysis. For the primary outcome variable (PAS) a linear model will be fitted to the data using PROC MIXED in SAS. The outcome will be a change in mean PAS score. Treatment will be included as a categorical variable. Additionally baseline PAS and other variables that will be identified as confounders will be included as covariates. Adjusted means in the two tDCS groups will be compared to those in

the sham group. To control for multiple testing, we will employ the Hochberg-Benjamini procedure, which will result in positive study result if both null hypothesis are rejected at the 0.05 level or one is rejected at the 0.025 level. Similar analyses will be performed on the FOIS, PCR, HLPE, and PDT outcomes. To assess the durability of the intervention effects, a repeated measures analysis will be used. The outcome will be FOIS score at the onset of the trial and at 1 month. Treatment time and their interactions will be included as categorical variables. Additionally other variables that will be identified as confounders will be included as covariates. Adjusted means at the onset of trial and 1 month in the two tDCS groups will be compared to those in the sham group at each time point. *Safety analyses* will be run on all subjects receiving at least one round of intervention. The incidence rates of adverse events will be described as a whole and by treatment group. Adverse events will be presented with and without regard to causality based on the investigator's judgment. *Interim Analyses* No formal efficacy analysis will be performed. The study will not be stopped for early efficacy or futility.

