Analytic plan for Secondary Aim: To assess the effect size across subject-specific predictors (baseline NIHSS score, dysarthria, CBT-lesion load and intubation), subgroup analyses will be conducted. For such analysis regression models will be employed that include intervention, covariate and covariate by treatment interactions as predictors and PAS scores, PCR, PDT, HLPE as outcomes, to examine the modifying effect of the covariates on the intervention. If a significant interaction is detected, analyses of major efficacy endpoints (PAS scores, PCR, PDT, HLPE) will be performed within each group.

Missing Data: Many longitudinal studies have the potential to suffer from problems with missing data. We anticipate a 35% - 40% attrition rate in this study, which includes drop-out, spontaneous recovery and discharge, based on review of our hospital records over the past 5 years. Based on experience, we do not expect any other serious problems with either the extent or the pattern of missing data but we will explore this issue by employing multiple imputation methods for handling missing data.

Sample Size and Power Calculations: We plan to enroll and randomize 99 subjects; 33 subjects to each of the two active and sham treatment. With the above sample size, after 40% attrition, we estimate that a difference of 1.0 and 1.15 standard deviations between the active and sham treatment in the mean primary outcome measure of the study can be detected with a type I error rate of 2.5% and power 80% and 90%, respectively. In our pilot study the difference we estimated was 1.35 with an approximate standard deviation for the differences in the two groups of 1.2, with a standardized difference of 1.1 standard deviations. Thus we expect to have $\geq 87\%$ power to detect the expected differences in our study. We also anticipate a greater effect size in the high dose group and thus the power to be greater.

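### No outcome model names the randomisation stratum: baseline PAS largely covers this in the primary model, but the FOIS durability and Secondary Aim models name neither term

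*Combined protocol and SAP*

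**What the plan says.** Section 3.1.1 sets the randomisation: "Subjects will be stratified based on their baseline PAS score (4-6 vs. 7-8) before randomization to the three treatment groups", using a "blocking scheme with block size of 6".

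Section 3.1.6 then treats severity differently from one analysis to the next:

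- **Baseline comparability.** Arms are compared "while accounting for stratification by dysphagia severity". This is the only analysis that mentions the stratification.
- **Primary PAS model.** "The outcome will be a change in mean PAS score". Treatment is categorical, and "Additionally baseline PAS and other variables that will be identified as confounders will be included as covariates".
- **Other swallowing outcomes.** "Similar analyses will be performed on the FOIS, PCR, HLPE, and PDT outcomes". The text does not say whether baseline PAS, the outcome's own baseline, or both are carried over.
- **FOIS durability model (onset and 1 month).** Treatment, time and their interactions are listed, then: "Additionally other variables that will be identified as confounders will be included as covariates". Neither baseline PAS nor the stratum is named.
- **Secondary Aim.** "regression models will be employed that include intervention, covariate and covariate by treatment interactions as predictors". The covariates are baseline NIHSS, dysarthria, CBT-lesion load and intubation. Again neither baseline PAS nor the stratum is named, although PAS is one of the outcomes.

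**The concern.** Stratified blocks balance the arms on severity, so the treatment contrast really does vary less than under simple randomisation. A model with no severity term does not know this. It leaves the between-stratum variation in the residual, and its standard errors come out too large. If severity is prognostic, tests become conservative and power is lost. With about 20 evaluable patients per arm after the planned attrition, there is little precision to spare.

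The clause on confounders is unlikely to close the gap. Those variables are to be found by comparing arms at baseline, and a factor balanced by design will seldom show an imbalance, however prognostic it is.

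There is a related gap in definition. Section 3.1.1 does not say which PAS is cut at 4-6 versus 7-8. Section 3.1.3 enrols on a single swallow scoring at least 4, while the outcome is a five-swallow mean. If the stratum is not a cut of that mean, the baseline PAS covariate captures it only in part.

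**Working it through.** **1. The plan's own power figure.** Inputs from Section 3.1.6: 33 per arm, 40% attrition, type I error 2.5%, differences of 1.0, 1.1 and 1.15 SD, with stated power of 80%, at least 87%, and 90%. Evaluable n = 33 × 0.6 = 19.8 per arm. By the normal approximation, two-sided 0.025, power = Φ(d√(n/2) − 2.241):

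- d = 1.0: Φ(3.146 − 2.241) = 81.7%
- d = 1.1: Φ(3.461 − 2.241) = 88.9%
- d = 1.15: Φ(3.618 − 2.241) = 91.6%

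The noncentral t with n = 20 gives 79.3%, 86.9% and 89.9%. The stated figures reproduce. They describe an unadjusted two-group comparison, so they do not depend on the stratum.

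**2. Is the stratum a function of the covariate?** Three score patterns possible under the bolus rules of Section 3.1.3 (withheld boluses score 8):

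- 1, 1, 8, 8, 8: mean 26/5 = 5.2, so stratum 4-6 by the mean but 7-8 by the worst swallow.
- 4, 3, 8, 8, 8: mean 31/5 = 6.2, in neither stratum as written.
- 4, 1, 1, 1, 1: eligible, but mean 8/5 = 1.6, below both strata.

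**3. Simulation of the choice of model.** From the plan: 99 patients, three arms, two strata, blocks of 6, 40% attrition. Assumed: attrition at random, residual SD 1, true effect 0 or 1.0, the baseline PAS distribution, the slopes, and how the stratum relates to mean PAS. Tests are two-sided at 0.025, with 6,000 runs per case. The third outcome type stands in for a physiological measure that depends on severity. Entries are power %, with type I error % in brackets.

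| Outcome; how the stratum is cut | Neither term | Baseline PAS | Stratum | Both |
|---|---|---|---|---|
| PAS, linear in baseline; mean | 64.5 (1.6) | 78.2 (2.4) | 73.9 (2.4) | 77.4 (2.4) |
| PAS, extra step at boundary; mean | 57.5 (1.2) | 76.9 (2.8) | 77.4 (2.4) | 78.3 (2.8) |
| Physiological; mean | 70.8 (1.7) | 75.9 (2.3) | 79.3 (2.4) | 78.0 (2.5) |
| PAS, linear in baseline; worst swallow | 59.5 (1.8) | 77.7 (2.5) | 68.7 (2.7) | 77.0 (2.5) |
| PAS, extra step at boundary; worst swallow | 56.1 (1.3) | 75.4 (2.5) | 74.6 (2.7) | 77.9 (2.7) |
| Physiological; worst swallow | 69.4 (1.7) | 72.7 (2.3) | 78.4 (2.5) | 77.4 (2.4) |

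The Monte Carlo standard error is √(0.025 × 0.975/6000) = 0.2 points for type I error and about 0.5 points for power.

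**4. Reading the table.**

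- *Primary PAS model, baseline PAS to both (four PAS rows).* Power changes by about −0.8, +1.5, −0.7 and +2.5 points. Type I error is 2.4-2.8% either way.
- *Neither term.* Type I error is 1.2-1.8%. Power is 56-71%, which is 7-22 points below the model with both terms and 8-20 points below the model with the stratum alone.
- *Mechanism.* With neither term, the average model standard error exceeds the true spread of the estimates by 4-11% (for example 0.376/0.357 = 1.05 and 0.412/0.370 = 1.11).
- *Bias.* Across all models the mean estimate lies within about 0.012 of the true value, so there is none to speak of.

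**5. Cost of an unneeded stratum term.** In the first row, (0.324/0.321)² = 1.019, about 2% more variance. A second simulation (20 per arm, residual SD 1.1, baseline slope −0.4, stratum means 4.2 and 6.3) gave variance ratios of 1.01, 0.99, 0.93 and 0.84 for residual stratum steps of 0, 0.5, 1.0 and 1.5 PAS points. The cost is therefore 1-2%.

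**The case against.** The strongest reply concerns the primary model. Baseline PAS is the variable the strata are cut from, in finer form, and adjusting for it is an accepted way to reflect stratified randomisation. Scoring withheld boluses as 8 raises the covariate too, so that jump is already in the linear term. The larger variance gains above (7% and 16%) need a step of 1.0-1.5 PAS points left over after adjustment. That is about the size of the whole pilot treatment difference of 1.35, and nothing in the documents supports it. All of this stands. A reader might infer from the missing stratum that the primary analysis does not follow the randomisation; the covariate sentence shows otherwise.

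A reader might also infer that the FOIS, PCR, HLPE and PDT analyses have no severity term. The text does not establish that. They are described as similar to a model that contains baseline PAS, and Section 6.1.2 adjusts the DSMB comparisons for the outcome's baseline value. Either covariate could be meant. The defect there is ambiguity.

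The replies are weaker for the other two analyses. In the durability model, onset FOIS is itself a response, so a comparison of changes would be partly self-adjusting; the plan, however, compares adjusted means at each time point. In the Secondary Aim regressions, a covariate such as baseline NIHSS may carry some dysphagia severity, but that is left to chance.

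**Conclusion.** The concern holds in a limited form. No outcome model names the stratum. For the primary PAS analysis this is minor: about −1 to +2.5 points of power, with type I error unchanged. For the FOIS durability model and the Secondary Aim regressions, neither baseline PAS nor the stratum is named. For the four parallel outcome analyses the covariate is unclear.

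If severity is prognostic, leaving out both terms gives conservative tests and a real loss of precision. It does not bias the estimates or inflate type I error, and the documents give no ground for inferring that it does.

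The figures rest on assumed baseline distributions, slopes and stratum definitions, and on attrition unrelated to arm or severity. They come from simple between-arm contrasts, not from the repeated-measures or interaction models themselves, so for those they show direction and rough size only. This is a low-severity point, worth making because the remedy is cheap.

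**What to change.** 1. In Section 3.1.6, add the two-level randomisation stratum as a fixed factor to the FOIS, PCR, HLPE and PDT models, the FOIS durability model and the Secondary Aim regressions.
2. In the same places, name the outcome's own baseline value as a covariate where applicable. In the durability model onset FOIS is already a response, so the stratum is the term to add.
3. In the primary model, list the stratum alongside baseline PAS as a low-cost option.
4. In Section 3.1.1, state which PAS defines the stratum (single worst swallow or five-swallow mean) and, if it is the mean, how values below 4 or between 6 and 7 are assigned.

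The cost is SAP wording and one degree of freedom per model, about 1-2% of variance if the stratum proves not to be prognostic. No change to design, data collection or sample size is needed.

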 - ii) Examining effects of differing doses of anodal tDCS versus sham stimulation on several physiological measures of swallowing, derived from videofluoroscopic swallowing studies;
 - iii) Evaluating durability of any observed effects of tDCS on dietary status as determined by changes in Functional Oral Intake Scale (FOIS) score at study onset and 1 month.
- B) We will assess safety by comparing the anticipated and observed incidence of the following major adverse events in each of the 3 groups: seizures, stroke specific mortality, neurological and swallowing deterioration as measured by changes in NIH Stroke Scale (NIHSS), and FOIS and PAS scores, respectively.

Secondary Aim: To investigate the impact of subject-specific predictors of dysphagia recovery on the outcome of our proposed intervention.

Approach: We will examine differences in the effect size of our intervention across different strata of subject specific-predictors extracted from our pilot model as well as corticobulbar tract (CBT)-lesion load (as a surrogate measure of lesion size and location) by performing a subgroup analysis using regression models.

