b) Hyoid, Laryngeal, and Pharyngeal excursion (HLPE): we will measure the actual excursion of these structures and landmarks from their resting point to maximal excursion. Hyoid, laryngeal and pharyngeal excursion are all important and semi-independent movements that close off the airway, shorten the pharynx, and open the upper esophageal sphincter, and thus are important variables to measure.

c) Pharyngeal Delay Time (PDT): will provide a temporal measure of the briskness of the swallow onset. We define PDT as “the time in centiseconds that the bolus is present in the hypopharynx before the swallow is triggered”. PDT will be measured from the time the bolus first passes the intersection of ramus of mandible and base of tongue, until the swallow begins - as seen by the final excursion of the hyoid bone associated with the swallow.

2. Dietary Outcome: Functional Oral Intake Scale [FOIS]: An important consequence of dysphagia is a compromised and altered diet. FOIS is a functional outcome that provides a validated measure of diet level. It has been tested and validated in stroke population and demonstrated to be sensitive to changes in swallowing functions in acute stroke patient. FOIS is an ordinal scale ranging from 1 (worst) to 7 (normal oral diet). It is easy to use and does not require specific training. It will be collected at four time points: 1) prior to initiating tDCS/sham stimulation (same day); 2) after the fifth session of tDCS/sham; 3) after the last session of tDCS/sham stimulation; and 4) by telephone at 1 month after the last stimulation session using a standardized questionnaire.

3.1.3

Protocol for Swallowing Evaluation

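### The FOIS durability model leaves out the end-of-treatment score, so on its own it cannot tell a lasting or fading effect from a late one, and its 1-month contrast forgoes baseline adjustment

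*Combined protocol and SAP*

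**What the plan says.** Section 2 lists, under the primary aim, "Evaluating durability of any observed effects of tDCS on dietary status as determined by changes in Functional Oral Intake Scale (FOIS) score". The sentence goes on to name study onset and 1 month as the two times.

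Section 3.1.6 (Analytic plan Primary Aim) carries this out: "To assess the durability of the intervention effects, a repeated measures analysis will be used". Then: "The outcome will be FOIS score at the onset of the trial and at 1 month". On the fixed effects: "Treatment time and their interactions will be included as categorical variables". On covariates: "Additionally other variables that will be identified as confounders will be included as covariates". On the contrasts: "Adjusted means at the onset of trial and 1 month in the two tDCS groups will be compared to those in the sham group"; this is done for both times. Baseline FOIS is thus a response. It is not named as a covariate, and no constraint of equal baseline means across arms is stated.

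Section 3.1.2 (Dietary Outcome) has FOIS collected four times, including "after the last session of tDCS/sham stimulation". Section 3.1.3 and the schedule table in Section 3.1.4 agree that there is an end-of-treatment score, on Day 5, and an interim one on Day 3. Neither enters the durability model.

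Just before the durability text, Section 3.1.6 says that FOIS will also be analysed along the lines of the PAS model, which takes change as outcome and baseline as covariate. It does not say at which time point.

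**The concern.** To say that an effect is durable, one normally needs to know that it was there when treatment stopped and how much of it remains later. The planned model sees the arms before treatment and at 1 month, with nothing in between. A positive 1-month result could be an effect that held, one that has partly faded, or one that emerged after treatment. A null 1-month result could mean an effect that was lost or one that never existed.

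Two smaller matters follow from the same choice. The onset contrast compares randomised groups before any treatment, so its expected value is zero and it says nothing about tDCS; Section 3.1.6 already has a separate baseline-comparability analysis. And because baseline is an unconstrained response, the named 1-month contrast gains little or nothing from it, in a trial that counts on about 20 completers per arm.

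**Working it through.** **Step 1. What the model can estimate.** Write the true effect versus sham as d5 at end of treatment and d30 at 1 month. The effect at onset is 0 by randomisation. The model yields an onset contrast (expected 0), a 1-month contrast (d30) and a treatment-by-time contrast (d30 − 0 = d30). The quantity d5 appears in none of them.

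| Course | d5 | d30 | Onset contrast | 1-month contrast | Treatment-by-time |
|---|---|---|---|---|---|
| Late onset | 0 | 0.5 | 0 | 0.5 | 0.5 |
| Held | 0.5 | 0.5 | 0 | 0.5 | 0.5 |
| Faded | 1.5 | 0.5 | 0 | 0.5 | 0.5 |

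Three different courses give the same planned results. The effect values are illustrative; the conclusion does not depend on them.

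**Step 2. Inputs for precision.** Section 3.1.6 gives 33 randomised per arm and 40% attrition: 33 × 0.6 = 19.8, about 20 per arm. As a check on that basis, a two-sample t-test with 20 per arm at two-sided 2.5% has power 79.3% at 1.0 SD, 89.9% at 1.15 SD and 86.9% at 1.1 SD. The plan states 80%, 90% and at least 87% for PAS, so its figures reproduce and are not in dispute.

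For FOIS the documents give no SD, effect size or correlation. The correlation rho between baseline and 1-month FOIS is therefore an assumption, shown from 0.3 to 0.7. Variances are taken as equal, and the seven-level scale is treated as continuous, as the plan does.

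**Step 3. Formulas** (variance in SD² units, n baselines and m one-month values per arm):

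- Planned 1-month contrast: 2[(1 − rho²)/m + rho²/n]. With n = m this is 2/m, the unadjusted comparison.
- Planned treatment-by-time contrast: 2[(1 − rho²)/m + (1 − rho)²/n].
- Baseline as covariate, or baseline means constrained equal: 2(1 − rho²)/m.

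Example, rho 0.5, n = 33, m = 20. Planned 1-month: 2[0.75/20 + 0.25/33] = 0.0902. Adjusted: 2 × 0.75/20 = 0.075. Ratio 0.83, a cut of 17%.

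**Step 4. Variance cut from baseline adjustment.**

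| rho | vs 1-month contrast, 20/20 | vs 1-month contrast, 33/20 | vs treatment-by-time, 20/20 | vs treatment-by-time, 33/20 |
|---|---|---|---|---|
| 0.3 | 9% | 6% | 35% | 25% |
| 0.5 | 25% | 17% | 25% | 17% |
| 0.7 | 49% | 37% | 15% | 10% |

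At rho 0 there is no gain over the 1-month contrast. A simulation at rho 0.5 with 33 baselines and 20 one-month values (20,000 runs) gave standard errors of 0.303 (1-month), 0.301 (treatment-by-time) and 0.278 (adjusted), against 0.300, 0.300 and 0.274 from the formulas.

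**Step 5. In terms of power.** Take a 1.0 SD FOIS effect (assumed), 20 complete pairs per arm, two-sided 2.5%, normal approximation. The planned 1-month contrast has 82% power at any rho. At rho 0.3, 0.5 and 0.7 the treatment-by-time contrast has 67%, 82% and 97%, and the adjusted analysis 86%, 92% and 99%.

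**The case against.** The case for the plan is substantial.

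- **The model matches the stated aim.** Section 2 frames durability as FOIS change between onset and 1 month. With two time points, the treatment-by-time term is exactly the between-arm difference in that change. This stands: there is no contradiction between aim and analysis. The gap is in what both of them leave out.
- **The plan is wider than this model.** A reader might infer that the trial cannot show whether an effect lasted. The documents do not support that. The 1-month comparison shows whether an effect is present then, and the separate FOIS analysis, if done at Day 5, would supply the end-of-treatment effect to set beside it. What remains is that its time point is not stated and no estimate of the change between the two effects is planned. The by-visit, baseline-adjusted comparisons in Section 6.1.2 are for the monitoring board, not the final analysis.
- **Baseline in the response is a standard form.** A reader might take it for an error or a source of bias. It is neither. With baseline means constrained equal it is about as efficient as a covariate. The loss comes from leaving them unconstrained.
- **The precision loss may be small.** It depends on an undocumented correlation, and entry on PAS ≥ 4 may narrow baseline FOIS and lower it. A mixed model that keeps dropouts' baselines recovers part of the loss. The number available at 1 month is also uncertain: the attrition figure includes discharge, while the 1-month FOIS is taken by telephone.
- **Missing 1-month scores.** Section 3.1.6 says multiple imputation will be explored, and an imputation model could use Day 5 FOIS. That would help with missing values, but would not add an end-of-treatment effect to the model.

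**Conclusion.** The point holds for the durability model, not for the plan as a whole. That this model alone cannot distinguish a held or faded effect from a late one follows from its outcome definition and needs no assumed figure. The onset contrast is uninformative but harmless.

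The precision point holds in direction for any correlation strictly between 0 and 1, but its size cannot be read from the documents. For the named 1-month contrast, the saving from baseline adjustment runs from 6–9% of variance at rho 0.3 to 37–49% at rho 0.7, the lower figure in each case being for 33 baselines and 20 one-month values. A reader might take the 49% as the cost of the plan. It is the favourable end: it needs a high correlation and complete pairs, and it ignores the treatment-by-time contrast, against which the saving at the same correlation is 15%.

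This concerns a secondary outcome. The primary PAS analysis, the sample size and the safety rules are untouched. It is a worthwhile improvement, not a flaw that threatens the trial.

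**What to change.** In Section 3.1.6, replace the durability paragraph along these lines:

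- Outcome: FOIS at end of treatment (after the last session) and at 1 month; Day 3 may be added.
- Baseline FOIS as a covariate; or keep it in the response with the arm means constrained equal at baseline.
- Treatment, time and treatment-by-time as factors.
- Report each dose versus sham at end of treatment and at 1 month, and the change in effect between them.
- Drop the comparison of arms at onset.
- State the time point of the separate FOIS analysis, or say that this model replaces it.

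Reword the durability item in Section 2 so that it names end of treatment as well as onset and 1 month.

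The cost is wording only. Every FOIS value needed is already scheduled, and the plan already uses baseline as a covariate for PAS.

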All participants will undergo 3 bedside swallowing evaluation and 2 standardized videofluoroscopic studies (VFSS) to further quantify dysphagia severity. The VFSS will be conducted by the SLPs at BIDMC according to established protocols. The first VFSS evaluation will occur on the day of first tDCS/sham stimulation session and the second evaluation will occur on the last (5th) day of stimulation. Prior to initiation of this project, the participating SLPs at BIDMC will undergo intensive training sessions with [name] (Boston University Medical Center) so that they can reliably detect deep penetration up to the vocal cords or aspiration (PAS score ≥ 4) on VFSS; patients will be enrolled if their PAS score ≥ 4 on at least one swallow. The SLP at BIDMC will not assign PAS scores which will be done by [name] team at their laboratory in Boston University Medical Center (BUMC). The de-identified and coded VFSS will be transferred electronically using a secure file transfer system on the same day to BUMC for detailed analysis and scoring. The lab at Boston University will be alerted immediately and will analyze the studies promptly to assess whether the PAS scores meet criteria for study enrolment. The patient will be viewed in the lateral plane for most swallows, but one swallow will be viewed in the anterior-posterior plane for asymmetry. The order of presentation will not be randomized but given in an incremental way due to the uncertainty about patient's swallowing status and for safety, as outlined below:

In Lateral view: One 5 ml Nectar Varibar Swallow, One 5ml Varibar pudding, 3 Varibar Thin Swallows: 5 ml thin liquids x1, 10 ml thin x 1, 30 ml thin x1;

10 ml & 30 ml thin liquids boluses are given only if no other boluses are aspirated

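### The secondary-aim interaction models do not list the baseline value of the outcome, so effect-modifier estimates are less precise than the collected data allow

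*Combined protocol and SAP*

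**What the plan says.** All references are to the combined protocol and SAP, section 3.

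- **Secondary-aim models** (3.1.6, Analytic plan for Secondary Aim): they are to "include intervention, covariate and covariate by treatment interactions as predictors and PAS scores, PCR, PDT, HLPE as outcomes". The lead-in names the candidate effect modifiers: "baseline NIHSS score, dysarthria, CBT-lesion load and intubation), subgroup analyses will be conducted". No Day 1 value of PAS, PCR, PDT or HLPE appears among the terms.
- **Primary model** (3.1.6, Analytic plan Primary Aim): "The outcome will be a change in mean PAS score", and "Additionally baseline PAS and other variables that will be identified as confounders will be included as covariates". The same paragraph adds "Similar analyses will be performed on the FOIS, PCR, HLPE, and PDT outcomes".
- **Baseline Comparability** (3.1.6), after describing the between-arm comparisons: "This comparison will allow us to identify potential confounders to be included in multivariate analyses".
- **Collection** (3.1.3): "The first VFSS evaluation will occur on the day of first tDCS/sham stimulation session", with a second study on day 5. The schedule in 3.1.4 lists PAS, PCR, HLPE and PDT on Day 1 and Day 5.
- **Randomization** (3.1.1): "Subjects will be stratified based on their baseline PAS score (4-6 vs. 7-8) before randomization".

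**The concern.** The plan treats baseline PAS as important enough to stratify on and to name in the primary model, but the models for the other stated aim do not list it, nor the Day 1 value of the three physiological outcomes. Interactions are the least precise quantities this trial will estimate. After the planned 40% attrition about 20 patients per arm remain, and a significant interaction is what triggers the within-group analyses. Leaving out a strong prognostic variable that is already scheduled for collection makes a weak analysis weaker, and that carries through to which subgroups are examined next.

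**Working it through.** **Inputs from the documents (3.1.6).** 99 randomized, 33 per arm; 40% attrition leaves 33 × 0.6 = 19.8, about 20 per arm; type I error 2.5%; pilot effect 1.35 / 1.2 = 1.125 SD, rounded in the plan to 1.1.

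**Assumptions.** The documents do not give the baseline-to-Day 5 correlation r, so 0.3, 0.5 and 0.7 are used. For the interaction test, two-sided alpha 0.05 and a binary modifier split 50/50 are assumed.

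**Step 1: the plan's own figures.** A two-sample t-test with 20 per arm and two-sided alpha 0.025 gives power of 79.3% at 1.0 SD, 89.9% at 1.15 SD and 86.9% at 1.1 SD. The plan states 80%, 90% and at least 87%, so its figures reproduce. They concern the primary pairwise comparison; the plan gives no figure for the interaction models.

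**Step 2: variance ratio from adding the baseline.** With equal variances at both times and a predictor uncorrelated with baseline, adjusted over unadjusted variance is:

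- Day 5 score: 1 − r²
- change score: (1 + r) / 2

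| r | Day 5: ratio | reduction | effective n × | Change: ratio | reduction | effective n × |
|---|---|---|---|---|---|---|
| 0.3 | 0.91 | 9% | 1.10 | 0.65 | 35% | 1.54 |
| 0.5 | 0.75 | 25% | 1.33 | 0.75 | 25% | 1.33 |
| 0.7 | 0.51 | 49% | 1.96 | 0.85 | 15% | 1.18 |

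Effective n is 1 / ratio. The two outcome forms run in opposite directions as r rises, so the form must be known before the gain can be sized.

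**Step 3: what this means for an interaction.** In outcome-SD units, with n = 20 per arm and a fraction f = 0.5 having the modifier:

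SE = √[2 × (1/(nf) + 1/(n(1 − f)))] = √[2 × (1/10 + 1/10)] = 0.632

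Detectable at 80% power = (1.960 + 0.842) × 0.632 = 1.77 SD. For a Day 5 score, multiplying by √(1 − r²) gives:

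| | no baseline | r = 0.3 | r = 0.5 | r = 0.7 |
|---|---|---|---|---|
| Detectable interaction (SD) | 1.77 | 1.69 | 1.53 | 1.27 |
| Power for 1.1 SD | 41% | 45% | 52% | 68% |

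**Step 4: a predictor correlated with baseline.** Simulation with 20 per arm, 4,000 runs, r = 0.5, predictor-baseline correlation 0.4 and no true modification:

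| Model | mean interaction | SD of interaction | mean predictor main effect |
|---|---|---|---|
| Day 5 score, no baseline | −0.012 | 0.335 | 0.204 |
| Change score, no baseline | −0.010 | 0.341 | −0.193 |
| Baseline added | −0.010 | 0.303 | 0.004 |
| Baseline and baseline-by-treatment | −0.015 | 0.335 | 0.008 |

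The interaction centres on about zero in every model. The variance reduction from adding baseline is 1 − (0.303/0.335)² = 18% for the Day 5 score and 1 − (0.303/0.341)² = 21% for the change, against 25% in Step 2. Omitting the baseline distorts the predictor's main effect, not the interaction.

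**Step 5: baseline severity itself modifies the effect.** Let the treatment effect change by −0.5 per SD of baseline, other settings as in Step 4. The predictor's interaction then shifts by −0.5 × 0.4 = −0.20. The simulation gives −0.204 (Day 5 score), −0.205 (change), −0.205 (baseline main effect added) and −0.004 (baseline-by-treatment term also added). Only the last model separates the predictor from baseline severity.

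**The case against.** **The plan may already cover it.** The models are said to include the listed terms, which does not exclude others, and the Baseline Comparability paragraph allows confounders to enter multivariate analyses. This does not close the gap. That route depends on observed differences between arms, so a strongly prognostic baseline value that happens to be balanced need not be picked up. The sentence extending the primary model to PCR, HLPE and PDT sits under the Primary Aim. No passage commits to baseline adjustment in the interaction models.

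**The gain may be small.** This stands in part. If the outcome is the Day 5 score and r is 0.3, the reduction is at most about 9%, and the PAS ≥ 4 entry criterion may lower r by restricting range. Correlation between predictor and baseline lowers the gain further. Even at r = 0.5, power for a 1.1 SD interaction reaches only 52%.

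**Adjustment is not free for every outcome.** This also stands. PCR, PDT and HLPE come from the first 5 ml thin-liquid swallow (3.1.3), and a bolus can be withheld for safety (3.1.2). The substitution of 8 applies to PAS only, so some Day 1 values of the other three may be missing.

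**A stronger reading.** A reader might infer that the unadjusted interactions are biased, because severe patients have more room to improve and the predictors are probably related to severity. The documents do not support that as a general claim. Treatment is randomized, so omitting a baseline main effect does not in general bias the treatment-by-predictor coefficient (Step 4). The room-to-improve mechanism needs baseline severity to modify the treatment effect as well as to correlate with the predictor, and then a baseline main effect alone does not remove it (Step 5).

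**Conclusion.** The concern holds as a precision point. The secondary-aim models leave out a covariate that the plan schedules and uses in its own primary model, and they do not say which form the outcome takes. For assumed r of 0.3 to 0.7, the variance of the interaction estimate could fall by up to 9% to 49% if the outcome is the Day 5 value, or by 35% down to 15% if it is the change. A realistic predictor-baseline correlation would reduce this: at r = 0.5 and a correlation of 0.4, the fall is about a fifth. These figures rest on assumed correlations, equal variances at the two times and a linear model, and none can be fixed from the documents. The weight is moderate: the analysis is a secondary one that remains imprecise after the change. It is worth making because it costs little and brings the secondary models into line with the primary one.

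**What to change.** In the Analytic plan for Secondary Aim:

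1. State for each of PAS, PCR, PDT and HLPE whether the outcome is the Day 5 value or the change from Day 1.
2. Add the Day 1 value of the same outcome as a covariate in every interaction model. With that covariate in a linear model, the Day 5 and change forms give the same interaction estimate.
3. As a sensitivity analysis, add a baseline-by-treatment term, to see whether an apparent modifier is standing in for baseline severity. Keep this out of the main model: in Step 4 it brought the SD of the interaction back to 0.335, the unadjusted Day 5 figure.
4. Say that missing Day 1 values of PCR, PDT or HLPE will be handled within the multiple imputation already foreseen in the Missing Data paragraph.

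The cost is SAP wording, one degree of freedom per main model and the handling of any missing Day 1 values. No new data are needed, and the primary analysis and sample size do not change.
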